4.3.3 Extension Phase

Not Applicable

4.3.4 End of Treatment (7 days after Treatment)

Patients will return to the study site within 7 days of study treatment (+2 days) for review of the eDiary assessment of medication compliance, and monitoring of tolerability and safety (including vital signs, laboratory tests, and electrocardiography). If a patient has NOT experienced a migraine headache of sufficient severity within 45 days after randomization, he or she will be withdrawn from the trial and instructed to return unused study medication and eDiary to the study center.

4.4 Post Study Access to Therapy (if applicable)

At the end of the study the sponsor will not continue to supply study drug to patients/investigators. The investigator should ensure that the subject receives the appropriate standard of care to treat the condition under study. Alternatively, patients may be eligible to receive study drug by participation in a rimegepant Long Term Safety study requiring approval by responsible health authorities and ethics committees.

5 POPULATION

Individuals entered in this trial will be patients who suffer from migraines. The treatment setting for these patients may include clinics, institutions or private office practices. Patients may be recruited through a variety of sources, including referral from physicians and other health care professionals.

5.1 Number of Subjects

It is anticipated that 1415 patients will need to be screened in order to randomize approximately 1200 patients. If, however, the minimum number of treated subjects is reached first, the study may be closed. The subjects will be randomized in a 1:1 ratio to the rimegepant or placebo treatment groups. It is anticipated that enrollment will occur at approximately 50 sites in the United States over a period of approximately 3 months during this trial.

5.2 Inclusion Criteria

1. Signed Written Informed Consent

- a) Written informed consent must be obtained from the patient in accordance with requirements of the study center's institutional review board (IRB) or ethics committee, prior to the initiation of any protocol-required procedures.

2. Target Population

Patient has at least 1 year history of migraines (with or without aura) consistent with a diagnosis according to the International Classification of Headache Disorders, 3rd Edition, beta version[1], including the following:

- a) Migraine attacks present for more than 1 year with the age of onset prior to 50 years of age
- b) Migraine attacks, on average, lasting about 4 - 72 hours if untreated
- c) Not more than 8 attacks of moderate or severe intensity per month within last 3 months
- d) Patients must be able to distinguish migraine attacks from tension/cluster headaches.
- e) Consistent migraine headaches of at least 2 migraine headache attacks of moderate or severe intensity in each of the 3 months prior to the Screening Visit and maintains this requirement during the Screening Period
- f) Less than 15 days with headache (migraine or non-migraine) per month in each of the 3 months prior to the Screening Visit and maintains this requirement during the Screening Period
- g) Patients on prophylactic migraine medication are permitted to remain on therapy provided they have been on a stable dose for at least 3 months prior to study entry.
- h) Patients with contraindications for use of triptans may be included provided they

meet all other study entry criteria.

3. Age and Reproductive Status

- a) Male and Female patients ≥ 18 years and older
- b) Women of childbearing potential (WOCBP) and non-sterile men must be using two acceptable methods of contraception to avoid pregnancy throughout the study in such a manner that the risk of pregnancy is minimized. See Section 5.5 for the definition of WOCBP. Males with vasectomy are considered surgically sterile provided the procedure occurred greater than 6 months prior to study participation
- c) No clinically significant abnormality identified on the medical or laboratory evaluation. A subject with a clinical abnormality or laboratory parameters outside the reference range may be included only if the investigator considers that the finding is not clinically significant and will not introduce additional risk factors and will not interfere with the study procedures
- d) At the Baseline Visit prior to dispensing Investigational Study Medication, WOCBP must have a negative serum or urine pregnancy test (minimum sensitivity 25 IU/L or equivalent units of HCG)
- e) Women must not be breastfeeding

5.3 Exclusion Criteria

1. Disease Target Exclusion

- a) Patient has a history of basilar migraine or hemiplegic migraine

2. Medical History and Concurrent Diseases

- a) Patient history of HIV disease
- b) Patient history with current evidence of uncontrolled, unstable or recently diagnosed cardiovascular disease, such as ischemic heart disease, coronary artery vasospasm, and cerebral ischemia. Patients with Myocardial Infarction (MI), Acute Coronary Syndrome (ACS), Percutaneous Coronary Intervention (PCI), cardiac surgery, stroke or transient ischemic attack (TIA) during the 6 months prior to screening.
- c) Uncontrolled hypertension (high blood pressure), or uncontrolled diabetes (however patients can be included who have stable hypertension and/or diabetes for 3 months prior to being enrolled)
- d) Patient has a current diagnosis of major depression, other pain syndromes, psychiatric conditions (e.g., schizophrenia), dementia, or significant neurological disorders (other than migraine) that, in the Investigator's opinion, might interfere with study assessments
- e) Patient has a history of gastric, or small intestinal surgery, or has a disease that causes malabsorption

- f) The patient has a history or current evidence of any significant and/or unstable medical conditions (e.g., history of congenital heart disease or arrhythmia, known suspected infection, hepatitis B or C, or cancer) that, in the investigator's opinion, would expose them to undue risk of a significant adverse event (AE) or interfere with assessments of safety or efficacy during the course of the trial
 - g) History of, treatment for, or evidence of, alcohol or drug abuse within the past 12 months or patients who have met DSM-V criteria[15] for any significant substance use disorder within the past 12 months from the date of the screening visit
 - h) Patients should be excluded if they have a positive drug screen for drugs of abuse that in the investigator's judgment is medically significant, in that it would impact the safety of the patient or the interpretation of the study results. In addition:
 - i) Detectable levels of cocaine, amphetamine, and phencyclidine (PCP) in the drug screen are exclusionary. Patients who are positive for amphetamines on the urine drug screen may have their urine samples evaluated for further analysis at the investigator's discretion to rule out a false positive result.
 - ii) Detectable levels of marijuana in the drug screen are not exclusionary, if in the investigator's documented opinion the patient does not meet DSM-V criteria[15] for substance use disorder, in the investigator's documented opinion, the positive test does not signal a clinical condition that would impact the safety of the patient or interpretation of the study results.
3. Allergies and Adverse Drug Reactions
- a) History of drug or other allergy which, in the opinion of the principal investigator, makes the subject unsuitable for participation in the study
4. Sex and Reproductive Status
- a) Females of child-bearing potential who are unwilling or unable to use an acceptable contraceptive method or abstinence to avoid pregnancy for the entire study period and for 56 days after the study.
 - b) Women who are pregnant or breastfeeding. Women with a positive pregnancy test on enrollment or prior to study drug administration
5. ECG and Laboratory Test Findings
- a) Estimated glomerular filtration rate (eGFR) according to the re-expressed abbreviated (four-variable) Modification of Diet in Renal Disease (MDRD) Study equation $\leq 40 \text{ ml/min/1.73m}^2$
 - b) Corrected QT interval $> 470 \text{ msec}$ (QTc by method of Frederica), during the Screening/Baseline Phase
 - c) Left Bundle Branch block
 - d) Right Bundle Branch Block with a QRS duration $\geq 150 \text{ msec}$.

- e) Intraventricular Conduction Defect with a QRS duration ≥ 150 msec.
 - f) Serum bilirubin (Total, Direct or Indirect) $> 1 \times$ ULN (Only abnormal values of between 1-1.5x ULN may be repeated once for confirmation during the screening period.)
 - g) Neutrophil count $\leq 1000/\mu\text{L}$ (or equivalent).
 - h) AST (SGOT) or ALT (SGPT) $> 1 \times$ ULN (Only abnormal values of between 1-1.5x ULN may be repeated once for confirmation during the screening period.)
6. Other Exclusion Criteria
- a) Prisoners or subjects who are involuntarily incarcerated
 - b) Subjects who are compulsorily detained for treatment of either a psychiatric or physical (e.g., infectious disease) illness
 - c) Exposure to non-biological investigational agents (other than rimegepant) within the 30 days prior to Baseline visit.
 - d) Exposure to biological investigational agents within the 90 days prior to Baseline visit.
 - e) Score of >0 on the Sheehan Suicidality Tracking Scale for the period of 30 days prior to Screening and during the study.
7. Please see Section 5.4 for Prohibited medications and Section 5.4.1 for allowable Rescue Medications

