4 STUDY PLAN

4.1 Study Design and Duration

This is a double-blind, randomized, multicenter, outpatient evaluation of the safety and efficacy of rimegepant as compared to placebo in the treatment of moderate or severe migraine. Participants will be dispensed one dose of study medication consisting of a rimegepant 75 mg tablet or a matching placebo. The total duration of the study will be approximately 11 weeks. This includes a 3-28 day Screening Period, an Acute Phase that can last up to 45 days or until the patient has a migraine that reaches moderate or severe intensity, followed by an End of Treatment Visit 7 days after the administration of the study medication.

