5.5 Women of Childbearing Potential

Women of childbearing potential (WOCBP) include any female who has experienced menarche and who has not undergone successful surgical sterilization (hysterectomy, bilateral tubal ligation, or bilateral oophorectomy) or is not postmenopausal. Post menopause is defined as:

1. Amenorrhea greater than or equal to 12 consecutive months without another cause and a documented serum follicle stimulating hormone (FSH) level > 35mIU/mL or
2. Woman with irregular menstrual periods and a documented serum follicle stimulating hormone (FSH) level > 35mIU/mL or

NOTE: FSH level testing is not required for women greater than or equal to 62 years old with amenorrhea of greater than or equal to one year

3. Woman on hormone replacement therapy (HRT)

Women of childbearing potential (WOCBP) and men must be using two acceptable methods of contraception to avoid pregnancy throughout the study and for up to 56 days after the last dose

of investigational product in such a manner that risk of pregnancy is minimized. It is required that all WOCBP use two methods of contraception for the duration of the study (i.e. beginning before treatment with the 1 dose of study medication to 56 days after dosing). The two methods should include one barrier method (ex. condom with spermicidal gel, intrauterine devices, cervical cap etc.) and one other method. The other method could include oral contraceptives or another barrier method (Note an Intra Uterine Device is considered one method).

Women who suspect that they have become or may have become pregnant despite using proper birth control methods, should use the home pregnancy test provided at Baseline Visit. Home pregnancy test should be administered prior to taking Investigational Study Drug. Patient should not take Investigational Study Drug if they are pregnant and patient should immediately contact Study Investigator.

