8.1.4 Pregnancy

If following the baseline visit, it is subsequently discovered that a study patient, or the female partner of a male study patient, is pregnant or may have been pregnant at the time of the investigational product exposure, including during at least 6 half-lives after the product administration, the investigational product will be permanently discontinued in an appropriate manner (i.e., dose tapering if necessary for patient safety). Protocol-required procedures for the study discontinued and the follow-up must be performed on the patient unless contraindicated by the pregnancy (i.e., x-ray studies). Other appropriate pregnancy follow-up procedures should be considered if indicated.

The investigator must immediately notify the Biohaven (or designee) Medical Monitor of the event and complete and forward the Pregnancy Form to Biohaven (or designee) within 24 hours and in accordance with SAE reporting procedures as described in Section 8.1.2. The pregnancy should be reported using paper forms, which should be faxed to

CCI

Follow-up information regarding the course of the pregnancy, including perinatal and neonatal outcome and, where applicable offspring information must be reported on a Pregnancy Report Form.

Any pregnancy that occurs in a female partner of a male study participant should be reported to the sponsor. Information on this pregnancy will be collected on the Pregnancy Report Form, as appropriate.

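### Protocol 5.2(3b), 5.3(4a) and 5.5 contradict each other on how many contraceptive methods are needed, whether abstinence counts, when the obligation ends, and which men it covers

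*Protocol*

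**What the plan says.** Three passages of the Protocol set contraception requirements.

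- **Section 5.2, inclusion 3b.** For non-sterile men and for women of childbearing potential (WOCBP), the rule is that they "must be using two acceptable methods of contraception to avoid pregnancy throughout the study in such a manner that the risk of pregnancy is minimized". No period after the study is given. The criterion refers to Section 5.5, but only for the definition of WOCBP.
- **Section 5.3, exclusion 4a.** Women of childbearing potential are excluded if they will not or cannot use "an acceptable contraceptive method or abstinence to avoid pregnancy for the entire study period and for 56 days after the study".
- **Section 5.5.** WOCBP and men, without the qualifier non-sterile, must use two methods of "contraception to avoid pregnancy throughout the study and for up to 56 days after the last dose". For WOCBP the period is then restated as "beginning before treatment with the 1 dose of study medication to 56 days after dosing". On the type of method: "The two methods should include one barrier method". Abstinence is not mentioned.

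No order of precedence among the three is stated. Section 5.7 says the sponsor grants no exceptions to the eligibility criteria. SAP 4.2 lists enrolment of subjects who do not meet those criteria as a significant protocol deviation.

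**The concern.** These are operative rules. Sites use 3b and 4a to decide eligibility, and all three passages bear on what a participant is told about contraception after exposure to an investigational drug. They differ on the number of methods, on whether abstinence is acceptable, on the end date and the event it is counted from, and on which men are covered.

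Two things are at stake. A site that takes 4a's acceptance of abstinence at face value may enrol a woman who does not meet 3b, and that is a significant deviation. In addition, the Protocol does not give sites one end date to pass on. In the schedule of assessments (Table 1) the last pregnancy test and the last planned contact are at the End of Treatment Visit, so what happens afterwards depends on the instruction given before or at that visit.

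**Working it through.** **Step 1: when does the study end?** Both 3b and 4a depend on this. Section 4.1 describes screening of up to 28 days and an acute phase of up to 45 days, "followed by an End of Treatment Visit 7 days after the administration of the study medication". Section 4.3.4 allows 2 further days for the visit.

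- Maximum duration with the visit on day 7: 28 + 45 + 7 = 80 days; 80 / 7 = 11.4 weeks.
- With the visit on day 9: 28 + 45 + 9 = 82 days; 82 / 7 = 11.7 weeks.

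The first figure reproduces the total of about 11 weeks stated in Section 4.1, so the study there ends at the End of Treatment Visit. If the study instead ran to 56 days after the dose, the total would be 28 + 45 + 56 = 129 days, or 18.4 weeks, which does not match.

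**Step 2: end of the obligation, in days after the single dose.** Let t be the day of the End of Treatment Visit.

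| Passage | Formula | t = 7 | t = 9 |
|---|---|---|---|
| 5.2(3b), read alone | t | 7 | 9 |
| 5.5 | 56 | 56 | 56 |
| 5.3(4a) | t + 56 | 63 | 65 |

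- 4a minus 5.5: (t + 56) − 56 = t, so 7 to 9 days.
- 5.5 minus 3b read alone: 56 − t, so 49 to 47 days.
- 4a minus 3b read alone: (t + 56) − t = 56 days for every t.

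Section 4.3.4 asks for the visit within 7 days, so t may be below 7. The 3b and 4a dates then move earlier together, and the 56-day gap between them does not change.

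**Step 3: method.**

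| Passage | Methods | Barrier required | Abstinence |
|---|---|---|---|
| 5.2(3b) | Two | Not stated | Not mentioned |
| 5.5 | Two | Yes, one | Not mentioned |
| 5.3(4a) | One, or abstinence | Not stated | Accepted |

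**Step 4: joint application.** A participant must meet every inclusion criterion and no exclusion criterion. A woman who is abstinent or uses one method is not excluded by 4a, but she does not meet 3b. Strictly she is ineligible, and the allowance in 4a changes nothing.

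**Step 5: men.** 3b covers non-sterile men and treats a vasectomy more than 6 months before participation as sterility; its period is the study. Section 5.5 covers men without that qualification, for up to 56 days after the last dose. A man with such a vasectomy is outside 3b but inside 5.5 as worded. 4a is a criterion for women only, so its silence on men is not a contradiction.

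**The case against.** The strongest defence is that the passages build on one another. Section 5.5 repeats 3b's period and extends it, so anyone who complies with 5.5 also complies with 3b, and 3b nowhere tells anyone to stop at the End of Treatment Visit. A site that applies everything would use two methods, one a barrier, for the longest period. Much of this stands. On that reading the explicit end-date conflict is only between 5.5 and 4a, 7 to 9 days, and day 7 to 9 for 3b is an inference from reading it alone.

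It does not remove the conflict. 3b cites 5.5 only for a definition, 4a does not cite it at all, and no precedence is given. One could take 5.5's restatement as redefining the study to run to day 56. That contradicts the duration of about 11 weeks and would push 4a to 56 + 56 = 112 days after the dose. Nor does taking the strictest rule explain why 4a accepts abstinence.

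A reader might also infer several stronger points that the documents do not support:

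- That a woman's eligibility is undetermined. It is not: she fails 3b, and the outcome differs only if a site relies on 4a alone.
- That the spread of end dates is 54 to 58 days. That figure pairs day 9 with day 63 and day 7 with day 65, giving one patient two visit dates. For any one patient it is 56.
- That Section 8.1.4, with "including during at least 6 half-lives after the product administration", is a further contraception clock. It defines when a discovered pregnancy counts as possibly exposed, for discontinuation and reporting, and does not conflict with a contraception period.
- That patients were in fact told different stopping dates. The consent pages are not among the documents reviewed, so this cannot be judged.

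**Conclusion.** The contradiction is real and lies within Protocol 5.2(3b), 5.3(4a) and 5.5. On method it is two (3b), two including a barrier (5.5), or one or abstinence (4a). On duration the explicit conflict is day 56 against about day 63 to 65. The 56-day difference between 3b and 4a arises only if 3b is read without 5.5. The coverage and period for men also differ between 3b and 5.5. The day counts assume that the study ends at the End of Treatment Visit, which the stated duration supports, and that this visit falls on day 7 to 9.

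The practical risk is an enrolment made on the strength of 4a that fails 3b, together with unclear instructions on the end date. This is an internal inconsistency worth correcting. It does not touch the endpoints, the analysis population definitions, sample size, power or the efficacy analysis.

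**What to change.** The sponsor should reconcile 5.2(3b), 5.3(4a) and 5.5 to a single consistent statement of:

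- the method requirement, including whether abstinence qualifies;
- the end date and the event from which it is counted;
- which men are covered and for how long.

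The consent wording should then be checked against that statement. Which rule is right is for the sponsor to decide, and none is proposed here. Section 8.1.4 need not change for this purpose.

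The cost is a text clarification, handled as a protocol amendment under Section 11, and a consent revision if the check shows a mismatch. Reconciling the text needs no new procedure, data collection or analysis.

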5.4 Prohibited Concomitant Medication

The below medications are prohibited prior to randomization and during the course of this study or as specified.

1. St. John's Wort should not be taken 14 days prior to randomization and throughout the study.
2. Butterbur root or extracts should not be taken 14 days prior to randomization and throughout the study.
3. History of use of ergotamine medications on greater than/equal 10 days per month on a regular basis for greater than/equal 3 months
4. History of non-narcotic analgesic intake on greater than/equal 15 days per month for greater than/equal 3 months
5. Use of narcotic medication, such as barbiturates, heroin, opium in the form of morphine and codeine, oxycodone and hydrocodone for at least 2 days prior to randomization.
6. Use of acetaminophen or acetaminophen containing products at daily dosing levels greater than 1000mg/day for at least two days prior to randomization.
7. Use of marijuana is prohibited during the study.

Patients on prophylactic migraine medication are permitted to remain on therapy provided they have been on a stable dose for at least 3 months prior to study entry.

5.4.1 Rescue Medications

After dosing with study medication, all other headache medication is prohibited during the 2 hours post dose. However, a patient who does not experience relief of their migraine headache at the end of two hours after dosing with study medication (and after the two hour assessments have been completed on the eDiary), will be permitted to use the following rescue medication: aspirin, ibuprofen, acetaminophen up to 1000mg/day (this includes Excedrin Migraine) naprosyn (or any other type of non-steroidal anti-inflammatory (NSAID)), antiemetics (e.g., metoclopramide or promethazine), or baclofen. These are the only medications allowed for rescue treatment after 2 hours post dose of study medication. However, if needed, after 48-hours of administering the one dose of study medication (and before coming in for the End of Treatment Visit) patients may take their prescribed standard of care medications for treatment of migraine (including triptans if not contraindicated, **provided all of the assessments have been completed on the eDiary**). Similarly, if the migraine is relieved by study medication at 2 hours after dosing but then recurs to a moderate or severe intensity level between two and forty-eight hours, the patient will be permitted to take the same rescue therapy as outlined above. In all circumstances, the patient will always continue to complete his or her eDiary for up to forty-eight hours after consuming the study medication. Use of concomitant medication after randomization, including rescue medication, will be recorded by the patient on a paper diary and reported to the site. The site will record medications that were taken within 14 days of dosing with study medication (or until the End of Treatment Visit).

